
among treatment features will be calculated in patient-specific utilities or part-worths associated with the attribute levels in the study. For other outcomes, participants will receive the following surveys via mail within 1-2 weeks after enrollment and prior to treatment initiation: SF-36, EPIC, AUA-SI, regret scale, CES-D, MAX-PC, SWD, PSQ-18, CPS, DCS and trust scale. Demographics, health and family history, clinical covariates and cancer progression data will be collected at 3, 6, 12 and 24 month follow-up. Histological tumor grade Gleason score and PSA and annual Elixhauser comorbidity score [257-258] will be obtained from the Pennsylvania Integrated Clinical and Research Database (PICARD), a UPHS, Fox-Chase Cancer Center electronic database, and PVAMC administrative and patient HER database. Retention and survey administration: During enrollment, importance of active participation will be emphasized. All participants will complete self-administered surveys at baseline within 1-2 weeks after enrollment (prior to treatment initiation) and again 3,6,12 and 24 months post-enrollment (see Appendix for copies of instruments, consent and medical chart review form). Non-respondents will be contacted via telephone after 10 days. In case of non-response due to death, cause of death will be noted and the physician investigators will determine cause of death (PCa or non-PCa related). The PCa conjoint analysis task, DCS, CPS and trust scale will be administered at baseline only, immediately after diagnosis of PCa and before treatment decision. D.2.4 Outcomes Assessment: D.2.4.1 As part of Specific Aim 2, following instruments will be used to measure preferences for participation in treatment decision, decision conflict and physician trust for both intervention group and the usual care control group at baseline, immediately after treatment decision, but prior to initiation of treatment. D.2.4.1.1 Control Preferences Scale (CPS): The CPS assesses the role that patients want to play and perceive playing in treatment decisions [259]. It consists of five sort-cards to assess different roles in decision making, ranging from a fully active to a fully passive role. This survey will be administered at baseline only. D.2.4.1.2 Decision Conflict Scale (DCS): The DCS is based on a conceptual framework of decision conflict, which is a state of uncertainty about which course of action to take. This scale is well studied in cancer area and has good psychometric properties [260]. We will administer this survey at baseline (before treatment). D.2.4.1.3 Patient Trust-Wake Forest Physician Trust Scale: This 10-item instrument is based on a multi-dimensional conceptual model of trust and measures trust in physicians and other health care providers [128-130]. Compared with previous scales, it showed improved internal consistency and variability [129, 131-132, 261]. Trust is measured by the sum of the 10 item scores, ranging from 10 to 50, with a higher score indicating higher trust [129, 131-132, 261]. D.2.4.2 As part of Specific Aim 3, the following outcomes will be measured for both intervention group and the usual care control group after initiation of treatment. D.2.4.2.1 Treatment choice: We will obtain data on primary and secondary treatments received, such as active surveillance, RP, RALP, EBRT, BT or PT via self report and verified from medical chart review. . D.2.4.2.2 Satisfaction with Decision (SWD): The SWD scale measures satisfaction with healthcare decisions. It was developed in the context of postmenopausal hormone-replacement therapy decisions. The six-item scale has excellent reliability (Cronbachs alpha = 0.88) [262]. D.2.4.2.3 Regret scale: Regret represents the unsettling feeling of having made a poor choice of treatment, persistent doubt, and a wish to change one's mind. The Regret scale is defined by three items that assess (1) the mans wish that he could change his mind about the kind of treatment he has received, (2) his feeling that he would be better if he had chosen the other treatment, and (3) whether he is bothered by the fact that other men received very different treatments for their PCa [33]. This scale exhibited good psychometric properties and has been extensively studied [33, 174, 263-265]. D.2.4.3 Following objective and subjective outcome measures will be assessed at baseline and at each post-treatment follow-up period (3,6,12 and 24 months) for intervention group and usual care control group. D.2.4.3.1 Biochemical recurrence: We will define progression of PCa as a change in PCa stage to an advanced stage or PSADT, post treatment [11, 44-45, 55, 160, 203]. We will obtain PSA data at baseline, prior to treatment, and post treatment at three months interval for 18 months. A PSA value of greater than 0.2 ng/ml indicates disease recurrence for surgery patients. For radiation therapy patients, we will adopt the Houston /Phoenix definition of the current PSA nadir + 2 ng/mL, with date of failure determined at call as the biochemical recurrence after radiation therapy [11, 44-45, 55, 160, 203]. Any treatment within six-month of diagnosis will be considered as adjuvant (review by investigators Drs. [name], [name], and [name]). D.2.4.3.2 Medical complications: We will identify complications that occur during either index or subsequent PRINCIPAL INVESTIGATOR (LAST, FIRST, MIDDLE): [name] PCORI Research Plan: Research Strategy 11 hospital admissions within 30 days of treatment [266]. Alibhai, et al. (2005), has grouped complications after RP into seven mutually exclusive categories: cardiac; respiratory; genitourinary; wound or bleeding; vascular; miscellaneous medical; and miscellaneous surgical [266]. Similarly, a list of complications for each treatment type will be developed by literature review and the physician investigators and consultants. D.2.4.3.3 Generic HRQoL- Medical Outcome Study Short Form: HRQoL data will be obtained using the Medical Outcome Study Short Form (SF-36) a multi-

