D.2.4.3.8. The Center for Epidemiologic Studies Depression (CES-D) scale: This 20-item, self-report scale to identify depression in the general population covers major components of depression, with an emphasis on affective components: depressed mood; feelings of guilt and worthlessness; feelings of helplessness and hopelessness; psychomotor retardation; loss of appetite; and sleep disorder [277].

D.2.4.4. Potential confounding variables: Disease severity: We will adjust for disease severity using information on PCa stage or TNM stage, grade and histology from electronic medical records. Gleason score: The Gleason score is a sum of the predominant pattern and the second most common pattern of the Gleason grade. Gleason score ranges from 2 -10 classified as low (2-4), intermediate (5-7) or high-grade (8-10). Elixhauser comorbidity index: The Elixhauser comorbidity index is a medical record-based metric designed to predict death in longitudinal studies, with an integer score representing increasing burden of illness [278]. We will use diagnostic information from inpatient encounters in 180 days prior to the month of PCa diagnosis to adjust for comorbidity, following the method of Elixhauser et al. [167,168,] and will obtain comorbidity scores using PICARD and VA inpatient and outpatient databases. Demographic variables: We will gather baseline data on patient age, income, education, health insurance, occupation, marital status, smoking status, height, weight and family history of PCa as possible covariates in our analyses.

Study duration

We will use stratified randomized control trial to study association between value markers and objective (complications and cancer recurrence) and subjective (HRQoL, psychological wellbeing) outcomes across intervention groups, over 24 month period. We will recruit newly diagnosed localized PCa patients from UPHS (Hospital of University of Pennsylvania, Presbyterian Medical Center, and Pennsylvania Hospital), Fox Chase Cancer Center and Philadelphia Veterans Administration Medical Center (PVAMC) and randomize them to conjoint analysis intervention ($n=360$) or control group ($n=360$). Length of a Subject's participation time In study: 24 months All participants will complete self-administered surveys at baseline within 1-2 weeks after enrollment (prior to treatment initiation) and again 3,6,12 and 24 months post-enrollment. Projected Date of the Proposed Study: July 2013 to June 2016.

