The sample will consist of 720 newly-diagnosed PCa patients. Inclusion criteria are: (1) treated for PCa at UPHS, Fox Chase Cancer Center or PVAMC; (2) aged 45 yearsr; (3) newly diagnosed with localized PCa and TNM stage T3a; (4) community dwelling; (5) Gleason score 8; (6) low (PSA 10 ng/ml, Gleason 6, clinical stage T1-2a), intermediate (PSA 10 -20 ng/ml, Gleason 7, clinical stage T2b), and high risk (PSA 20, Gleason 8, clinical stage T2c-3a) group [45] and (7) provide informed consent.

Key exclusion criteria

Exclusion criteria are: (1) Distant, metastatic or un-staged PCa at diagnosis; (2) visited the clinics to obtain second opinion only; (3) moved to another location; (4) unable to communicate in English and (5) cognitive impairment (Mini Mental State Exam or MMSE score ≤ 21). MMSE is a standardized mental status examination widely used for clinical and research purposes [197,198].

Vulnerable Populations

Children Form

Pregnant women (if the study procedures may affect the condition of the pregnant woman or fetus) Form

Fetuses and/or Neonates Form

Prisoners Form

Other

None of the above populations are included in the research study

The following documents are currently attached to this item:

There are no documents attached for this item.

Populations vulnerable to undue influence or coercion

NA

Subject recruitment

Participants will be recruited from UPHS, PVAMC and Fox Chase Cancer Center's urology and radiation oncology clinics using recruitment protocols that we have successfully used in our prior and ongoing PCa studies. Recruitment will occur in seven steps: 1) determining potential eligibility; 2)

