patients in decision (measured using CPS) using multi-nominal regression model to adjust for observed covariates. Then we will examine if these associations vary across intervention and usual care control groups. We then will repeat the model with other independent variables (decision conflict and trust). Next, we will test the association denoted by path c (direct effect of DCS, CPS, and trust on outcomes). For continuous outcomes (HRQoL, AUA-SI, MAX-PC, CES-D, SWD, and PSQ-18), we will compute area under the curve (AUC) for each measure for each patient. We will analyze AUC summaries with univariate linear models. In our main analysis we will analyze the series of functional status measures using linear mixed models that predict the outcome from time, independent variables and their interaction. We will repeat the analyses described for path c, this time by including treatment received in the models. We will test if the observed effects of DCS, CPS or trust on outcomes will be weaker after controlling for treatment. These analyses will be performed within and between groups (intervention and usual care controls). Specific Aim 3: Hypothesis: Prostate cancer patients in the intervention group undergoing conjoint analysis-value clarification exhibit improved treatment choice, satisfaction with decision, lower regrets, and improved objective and subjective outcomes. Analysis for Specific Aim 3 uses intent-to-treat approach: all randomized participants will be included regardless of whether they drop out of the intervention or study. Analysis will involve comparison of the primary outcomes between intervention and usual care control groups. Improved treatment choice is operationalized as the likelihood of low-risk PCa patients receiving active surveillance than active treatment, and will be compared between intervention and usual care control group. To allow for different trajectories of the outcome measures and to afford flexibility in making contrasts within participants over time and across participants, while simultaneously controlling for potential confounders, we propose the participant-specific or mixed effects linear model, in which the mean outcome depends on fixed covariates and random effects. The primary fixed effects will be indicators for intervention group and hospital. We will also stratify the analysis by type of treatment. The random effects represent the unobserved factors that lead to variation of the individual participants outcome. Random intercepts for each participant permit modeling of natural variation across participants at baseline. In addition, random slopes or random effects for the trajectory of each participant over time, allow for variation of each participant about a mean, overall trajectory across all participants. Although less robust to model misspecification, the mixed effects paradigm offers special flexibility in longitudinal data when exposures vary over time and when dropout and missed visits lead to unbalanced groups. The target of inference is the participant-specific response to treatment over time. At each time point of interest, we will estimate from the fitted model the difference from baseline in outcome for the treatment and control groups and test the difference between these differences. Both univariate and multivariate results will be reported in terms of Wald test, point estimates, and 95% confidence intervals. Specific Aim 4: Hypothesis 4: Prostate cancer patients whose treatment is more concordant with their values markers will experience improved subjective and objective outcomes. This specific aim s for intervention group only. We will analyze the association of the concordance between stated individual preferences and actual treatment received with objective (PCa recurrence and complications), subjective (HRQoL, psychological wellbeing, SWD, and satisfaction with care) outcomes, across treatment groups, adjusting for covariates. Association between the value markers (profiles) and measures of outcomes and personal and clinical characteristics: The value markers will be studied for their relationship with socio-demographic and clinical characteristics. We will also assess the association of value markers with outcomes. We will perform logistic regression with outcomes as the dependent variable and dummy variables for the utility-based profiles obtained earlier as independent variables. We will perform this evaluation with and without adjusting for patient attributes in the logistic model. For each case (adjusting and not adjusting for patient attributes), the evaluation of association between these profiles and outcomes will be based on a likelihood ratio test of the set of odds ratios corresponding to the dummy variables of the profiles. Additionally, we will perform a sequence of pair wise tests of comparisons of the profiles in terms of the proportion of type of treatment received based on the Holms multiple comparisons approach. This procedure is hierarchical in that it will identify the utility-based profile at the start of the process before making other comparisons, thus protecting the Type I error from additional comparisons. Specifically, Holms approach tests each pair-wise comparison in ascending order of p-values. Successively larger p-values have less rigorous alpha. The sequential Holm tests terminate after the first non-significant comparison so no subsequent comparison is significance. Concordance and its assessment: Understanding and respect for the patients preference and values is the main aspect of concordance [69, 73]. Thus a first step in concordance involves the physician extracting and understanding the patients view, followed by an agreement between the physician and patient regarding a management plan that integrates their views. There exist many definitions of concordance. For the purpose of this study, we operationalized concordance as agreement between a patients value markers and the attributes (or characteristics) of the treatment that

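### The only Gleason coding given for confounder adjustment puts scores 6 and 7 in one band, although the protocol's own risk groups separate them; used in the non-randomised analyses, it leaves that difference unadjusted.

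*Combined protocol and SAP*

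**What the plan says.** D.2.4.4 (Potential confounding variables), repeated under Primary outcome variable(s), defines the Gleason covariate: "classified as low (2-4), intermediate (5-7) or high-grade (8-10". The same section commits to severity adjustment in a separate sentence: "We will adjust for disease severity using information on PCa stage or TNM stage, grade and histology from electronic medical records". It names neither PSA nor a composite risk group as a severity covariate.

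Key inclusion criteria and D.2.1.1 (Participants) group men differently: "low (PSA 10 ng/ml, Gleason 6, clinical stage T1-2a), intermediate (PSA 10 -20 ng/ml, Gleason 7, clinical stage T2b", and then "high risk (PSA 20, Gleason 8, clinical stage T2c-3a) group". Each group is described by PSA, Gleason and clinical stage together. A separate criterion reads "5) Gleason score 8".

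D.2.3 (Data collection and follow-up) shows that the raw values will be available: "Histological tumor grade Gleason score and PSA and annual Elixhauser comorbidity score" are to be taken from the institutional databases.

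No section reconciles the two groupings, and none says whether the band or the numeric score is the model term.

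**The concern.** Background section A.6 presents active surveillance as a strategy for low-risk disease, and A.6.1 says that severity bears on outcome and has to be taken into account when outcomes are evaluated. On the protocol's own account, risk level is tied to both treatment received and outcome, which is what makes it a confounder.

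Several planned analyses depend on covariate adjustment. Aim 2 relates decision conflict, trust and role preference to treatment received and to outcomes. Aim 4 relates concordance to outcomes within the intervention arm only. The propensity model predicts which of six treatments a man receives. None of these contrasts is randomised.

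The Analysis Plan makes propensity balance conditional on having all relevant covariates in the model, and checks it by comparing t-statistics for those covariates before and after adjustment. If the covariate is the band, an imbalance between Gleason 6 and Gleason 7 is neither adjusted for nor visible to that check.

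**Working it through.** No stated sample size, power or alpha depends on this point, so there is no figure of the plan to reproduce. The check compares category boundaries and then illustrates the size.

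**Step 1. Map the scores.** Comparison signs appear to be missing from the criteria as read, so low is taken as 6 or less and high as 8 or more. The literal values 6, 7 and 8 give the same result.

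| Gleason | D.2.4.4 band | Risk group by Gleason criterion |
|---|---|---|
| 2-4 | low | low |
| 5-6 | intermediate | low |
| 7 | intermediate | intermediate |
| 8-10 | high-grade | high |

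Only the boundary between 7 and 8 agrees.

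**Step 2. How much of the 7 versus 6-or-less split does the band carry?** Take men with Gleason 7 or less. Let q be the share scoring 2-4 and p the share scoring 7; neither is in the documents. Within the 5-7 band the share scoring 7 is m = p/(1 - q). The fraction of the variance of the 7 versus 6-or-less indicator explained by the band is 1 - (1 - m)/(1 - p).

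- q = 0: 0%.
- q = 1%, p = 30% to 50%: 0.4% to 1.0%.
- q = 5%, p = 30% to 50%: 2.3% to 5.3%.
- q = 10%, p = 30% to 50%: 4.8% to 11.1%. For p = 50%, m = 0.5/0.9 = 0.556 and 1 - 0.444/0.5 = 0.111.

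The band carries little of the distinction anywhere in this assumed range.

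**Step 3. Size of the bias.** Within the band, bias = (difference in Gleason 7 share between the compared groups) x (outcome gap between Gleason 7 and Gleason 6). Both inputs are assumptions.

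- Imbalance 10 points, recurrence gap 5 points: 0.10 x 0.05 = 0.5 points.
- Imbalance 30 points, recurrence gap 15 points: 0.30 x 0.15 = 4.5 points.

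**Step 4. One worked case inside that range.** Assume recurrence of 5% at Gleason 6 and 15% at Gleason 7. Assume concordant men are 60/30/10 and discordant men 40/50/10 at Gleason 6/7/8. Recurrence within the band is:

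- concordant: (0.6 x 0.05 + 0.3 x 0.15)/0.9 = 8.33%;
- discordant: (0.4 x 0.05 + 0.5 x 0.15)/0.9 = 10.56%.

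The difference is 2.2 points within the band, or 0.9 x 2.2 = 2.0 points over all men. Halving the imbalance (55/35/10 against 45/45/10) gives (0.45 - 0.35)/0.9 x 0.10 = 1.1 points within the band, or 1.0 overall. Gleason 8 is held at 10% in both groups, so all the confounding sits inside the band by construction. None of these figures allows for stage.

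**The case against.** The strongest reply is that the plan never makes the band the model term. The D.2.4.4 sentence describes the scale, the adjustment sentence refers only to grade, and the propensity model uses unspecified baseline factors. An analyst could enter the numeric score without departing from the text. This stands, and it is why the point is conditional. A reader might infer that residual confounding has been accepted by choice; the documents do not support that. Even so, the band is the only coding they offer.

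Second, a reader might infer that the whole adjustment set is blind to low versus intermediate risk. It is not. Stage is an explicit covariate, and T1-2a against T2b separates some of these men. Baseline PSA is collected and could enter the propensity model. What remains is that men of the same stage can differ in Gleason score, and that PSA is not listed as a severity covariate. The instrumental-variable analysis targets unobserved bias, but its stated instrument is for treatment received, not for concordance or the Aim 2 decision measures.

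Third, it is tempting to extend the point to Aim 3, because "Improved treatment choice is operationalized as the likelihood of low-risk PCa patients receiving active surveillance than active treatment". That is a randomised intent-to-treat comparison, and the eligibility text supplies its own definition of low risk. The covariate bands neither define that subset nor threaten the comparison.

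Fourth, the bias may be small against precision. Aim 4 uses 360 men. With an even concordance split (assumption) and 90% in the band, that is 162 against 162. The standard error at 8.33% and 10.56% is about 3.2 points, so 2.2 points is about 0.7 standard errors. The Accrual section also names HRQoL as the primary outcome, and no HRQoL bias is quantified here. Both remarks are fair and limit the weight. They are not reasons to keep the coding.

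**Conclusion.** The mismatch is real and holds under either reading of the eligibility values: the stated coding merges Gleason 6 and 7, and the protocol's risk groups do not. If that coding is used in Aim 2, Aim 4 or the propensity models, the Gleason part of the low versus intermediate difference goes unadjusted and unchecked, with stage recovering part of it.

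The size is not known from the documents. The range of 0.5 to 4.5 points of recurrence rests wholly on assumed imbalances and gaps, before stage adjustment, and the single case of 2.2 points should not be read as an estimate. Two further inferences go beyond the text. One is that Gleason separates surveillance candidates better than PSA or stage does; the documents do not rank the three. The other is that the bands reduce in practice to 5-7 against 8; that needs few men scoring 2-4 and none above 8, and the documents give no score distribution. The merger of 6 and 7 depends on neither.

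This is worth correcting because it is an inconsistency in a named confounder that costs nothing to remove. It does not undermine the randomised comparison.

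**What to change.** In D.2.4.4 and the Analysis Plan, replace the 2-4 / 5-7 / 8-10 bands. For the Aim 2 and Aim 4 outcome models and the propensity models, state that Gleason enters either as the numeric score or as 6 or less / 7 / 8 or more, together with baseline PSA and clinical stage. Alternatively, use the protocol's own low, intermediate and high risk group, stating how a man is classified when his PSA, Gleason and stage point to different groups. Run the propensity balance check on the same terms.

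The cost is a recode of data already being collected. Three levels replace three levels, so the Gleason term uses no more degrees of freedom than before (a linear numeric term uses fewer). No visit, sample size or power figure changes.
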